4.3 Alternatives

Alternatives to participation in this study include:

- Getting treatment without being in a study which may include other Merkel cell carcinoma therapy such as:
 - o Immunotherapy without radiotherapy

- o Chemotherapy
- o Targeted therapy
- o Radiotherapy alone without immunotherapy
- Taking part in another study
- Getting no treatment
- Getting comfort care, also called palliative care. This type of care helps reduce pain, tiredness, appetite problems and other problems caused by the Merkel cell carcinoma. It does not treat the cancer directly but instead tries to improve how you feel. Comfort care tries to keep you as active and comfortable as possible.

5. INVESTIGATIONAL AGENT/DEVICE/PROCEDURE INFORMATION

5.1 Investigational Agent/Device/Procedure

5.1.1 Pembrolizumab

Unit: Pembrolizumab 200 kg; comes in 100 mg/4mL solution vials

Route: Intravenous infusion

Source: Stanford Hospital Pharmacy

5.1.1.1 Handling and Dispensing

Pembrolizumab must be stored refrigerated (2°C - 8°C) with protection from light. In preparation of infusion, pembrolizumab may be stored in IV infusion bags (PVC, non-PVC/non-DEHP) or glass infusion containers at room temperature for up to 6 hours or refrigerated (2°C - 8°C) for up to 24 hours. Drug must be completely delivered to the subject within 24 hours of preparation. This includes any time in transit plus the total time for the infusion.

As with all injectable drugs, care should be taken when handling and preparing pembrolizumab. Whenever possible, it should be prepared in a laminar flow hood or safety cabinet using standard precautions for the safe handling of intravenous agents, applying aseptic technique. Latex gloves are required. If pembrolizumab concentrate or solution comes in contact with skin or mucosa, immediately and thoroughly wash with soap and water.

5.1.1.2 Preparation and Administration of Pembrolizumab

Pembrolizumab will be prepared according to standard of care and administered intravenous at a dose of 200 /kg according to standard of care. See the current package insert for additional details.

Pembrolizumab should be administered under the supervision of a physician experienced in the use of intravenous agents. Pembrolizumab is administered as an intravenous infusion only. Patients may be premedicated as per standard of care as needed. Infusions will be interrupted, or the rate slowed as needed for mild or moderate (grade 1 or 2) infusion-related reactions. Infusions will be permanently stopped for severe or life-threatening (grade 3 or 4) infusion reactions.

5.1.1.3 Criteria that Require Permanent Discontinuation of Pembrolizumab

Subjects MUST discontinue study treatment for any of the following reasons that are not related to a related adverse event:

- Withdrawal of informed consent (subject's decision to withdraw for any reason)
- Pregnancy
- Loss of ability to freely provide consent through imprisonment or involuntary incarceration for treatment of either a psychiatric or physical (e.g., infectious disease) illness.

Exceptions to Permanent Discontinuation of pembrolizumab dosing under the following situations:

- Potentially reversible inflammation (< Grade 4), attributable to a local antitumor reaction and a potential therapeutic response. This includes inflammatory reactions at sites of tumor resections or in draining lymph nodes, or at sites suspicious for, but not diagnostic of metastasis.
- Hospitalization for < Grade 2 adverse events where the primary reason for hospitalization is to expedite the clinical work-up.
- Subjects with the following conditions where in the investigator's opinion continuing study drug administration is justified:
 - Ocular toxicity that has responded to topical therapy
 - Endocrinopathies where clinical symptoms are controlled with appropriate hormone replacement therapy.

Note: Pembrolizumab may not be restarted while the subject is being treated with systemic corticosteroids except for subjects on stable doses of hormone replacement therapy such as hydrocortisone.

All subjects who discontinue treatment prematurely due to a drug-related AE or symptomatic progression prior to disease assessment at the end of treatment visit are required to return for the 3 weeks (± 1 week) after the last dose of pembrolizumab visit, unless they are switched to an alternate anti-neoplastic medication.

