- The appearance of new lesions in subjects with other stable or shrinking baseline tumor burden may be experiencing clinical benefit and should continue on treatment before alternative anti-cancer agents are considered. These subjects can be seen to have continued tumor shrinkage in subsequent imaging.
- As long as overall tumor burden is stable or decreasing, subjects can remain in treatment, even in the presence of new lesions, at the discretion of the treating physician.
- Clinical progression warranting alternative anti-cancer treatment should be considered in subjects whose overall tumor burden appears to be substantially increased and/or in subjects whose performance status is decreased.

- Follow-Up

- Subjects with SD, PR or CR will continue receiving pembrolizumab every 3 weeks per standard of care. After the last dose of pembrolizumab, subjects will enter Follow-Up. Efficacy assessments for these subjects are per standard of care.

- Survival Follow-Up (Post Study Follow-Up)

- Subjects who are no longer receiving pembrolizumab due to unacceptable toxicity (e.g., refractory Grade > 3 AEs), disease progression, investigator judgment, or study closure are managed in survival follow-up.

- If possible, subjects will be contacted or medical records reviewed every 6 months (± 2 weeks) for 5 years after the last dose of pembrolizumab to evaluate survival status.

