6. DOSE MODIFICATIONS

Decisions to skip or modify a pembrolizumab dose will be made based on specified safety criteria as shown in the table below.

Recommended Dose Modifications of Pembrolizumab for Adverse Reactions

Treatment-Related Adverse Reaction	Severity of Adverse Reactions*	Dose Modification
Immune-Mediated Pneumonitis	Grade 2 pneumonitis	Withhold (a)
	Grade 3 or 4 pneumonitis or recurrent Grade 2 pneumonitis	Permanently discontinue.
Immune-Mediated Hepatitis	Aspartate aminotransferase (AST)/or alanine aminotransferase (ALT) more than 3 and up to 5 times the upper limit of normal or total bilirubin more than 1.5 and up to 3 times the upper limit of normal	Withhold Pembrolizumab. Resume Pembrolizumab in patients with complete or partial resolution (Grade 0 to 1) of hepatitis after corticosteroid taper.
	If no liver mets, AST or ALT more than 5 times the upper limit of normal or total bilirubin more than 3 times the upper limit of normal; if liver mets and grade 2 AST or ALT at baseline with at least 50% increase that persist for one week or more	Permanently discontinue.
Immune-Mediated Colitis		Withhold.
	Grade 2 or 3 diarrhea or colitis	Resume in patients with complete or partial resolution (Grade 0 to 1)

		of colitis or diarrhea after corticosteroid taper.
	Grade 4 diarrhea or colitis or recurrent Grade 3 diarrhea or colitis	Permanently discontinue.
Immune-Mediated Endocrinopathies (including but not limited to hypothyroidism, hyperthyroidism, adrenal insufficiency, hyperglycemia)	Grade 3 or 4	Withhold until clinically stable.
Immune-Mediated Nephritis and Renal Dysfunction	Grade 2	Withhold. Resume in patients with complete or partial resolution (Grade 0 to 1) of nephritis and renal dysfunction after corticosteroid taper.
	Grade 3 or 4	Permanently discontinue.
Other immune-mediated adverse reactions (including but not limited to myocarditis, myositis, psoriasis, arthritis, hypopituitarism, uveitis, Guillain-Barré syndrome, pancreatitis, rhabdomyolysis, myasthenia gravis, histiocytic necrotizing lymphadenitis, demyelination, vasculitis, hemolytic anemia, hypophysitis, iritis, and encephalitis) For Immune-mediated	For any of the following: Grade 2 or 3 based on severity and type Grade 3 based on severity and type or grade 4 Grade 3 or suspected Stevens-Johnson syndrome (SJS) or toxic epidermal necrolysis	Withhold (a) Permanently discontinue. Withhold

skin AEs	(TEN) Grade 4 or confirmed SJS or TEN	Permanently discontinue.

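### Grade 3 inflammation at a tumor site can be a permanent stop and a DLT under Section 6, or neither under the exception in Section 5.1.1.3

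*Combined protocol and SAP*

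**What the plan says.** Four places in the protocol bear on when toxicity ends pembrolizumab for good.

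- **Section 5.1.1.3** opens its stop list with "Subjects MUST discontinue study treatment for any of the following reasons that are not related to a related adverse event". The three reasons are withdrawal of consent, pregnancy, and incarceration. A second list follows, headed "Exceptions to Permanent Discontinuation of pembrolizumab dosing under the following situations". Its first item is "Potentially reversible inflammation (< Grade 4), attributable to a local antitumor reaction and a potential therapeutic response", and the text continues: "This includes inflammatory reactions at sites of tumor resections or in draining lymph nodes, or at sites suspicious for, but not diagnostic of metastasis".
- **Section 6** states: "Decisions to skip or modify a pembrolizumab dose will be made based on specified safety criteria as shown in the table below". In the immune-mediated pneumonitis row, the entry for "Grade 3 or 4 pneumonitis or recurrent Grade 2 pneumonitis" is permanent discontinuation. The table does not mention Section 5.1.1.3 or a local antitumor reaction.
- **Section 6, DLT definition**, makes an event a DLT when therapy is permanently stopped for toxicity as the table defines it, or when the patient withdraws because of toxicity that he or she finds unacceptable.
- **Section 4.2** has its own mandatory stop for any adverse event that, in the investigator's opinion, makes continuing not in the patient's interest.

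Section 1.1 names safety as the first primary objective. Sections 12.3.2 and 12.4.2 plan continuous monitoring of toxicity rates and a final toxicity count. They give no DLT threshold.

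**The concern.** Every patient is irradiated at one or two disease sites between the first and second cycles (Section 5.1.2), so inflammation at a tumor site can plausibly arise in this trial. If it is Grade 3 and in the lung, the protocol gives two answers to whether pembrolizumab is permanently stopped, and the DLT label follows that answer.

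What separates the two is whether the investigator attributes the inflammation to an antitumor reaction and a possible response. No criteria are given for that attribution, and it is made open-label. A judgement of benefit can therefore decide whether a toxicity is counted, in a trial whose first question is whether the combination is safe. Two patients with the same event could also be managed differently.

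**Working it through.** No design figure in the plan belongs to this point. The check is a comparison of text, followed by one piece of arithmetic.

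**1. What the exception acts on.** The stops listed just above it in Section 5.1.1.3 are not adverse events, and inflammation cannot be an exception to pregnancy or incarceration. The exception must act on adverse-event stops elsewhere, of which there are two: Section 4.2 and the Section 6 table. Section 4.2 already leaves the decision to the investigator, so an exception that rests on the investigator's attribution changes little there. It changes the result in Section 6, where the stop is set by event type and grade.

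**2. Where the grades overlap.** Below Grade 4 includes Grades 2 and 3. The pneumonitis row stops permanently at Grade 3, Grade 4 and recurrent Grade 2. The conflict is therefore at Grade 3 and recurrent Grade 2. At Grade 4 the exception does not apply, and a first Grade 2 event is only withheld.

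**3. Whether Section 6 absorbs the exception.** It does not. One permanent-discontinuation entry, for life-threatening reactions, expressly leaves out endocrinopathies, which also have an exception in Section 5.1.1.3. Nothing comparable is written for local inflammation.

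**4. Consequence for one event: Grade 3 pneumonitis at a tumor site.**

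| | Section 6 table followed | Section 5.1.1.3 exception applied |
|---|---|---|
| Permanent discontinuation | Yes | Not required |
| DLT | Yes | No, unless the patient withdraws for toxicity or another entry is met later |
| Deciding factor | Type and grade | Investigator attribution, no criteria |

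The exception can take events out of the DLT count and cannot add any, so the effect relative to the table is in one direction.

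**5. Size.** Planned n = 30 (Section 12.5). One reclassified patient changes the proportion by 1/30 = 0.033, or 3.3 points.

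As an illustration with **assumed** counts, suppose four patients meet a permanent-discontinuation entry and two of them are kept on drug under the exception. Use Wilson's interval, the plan's method for proportions, with z = 1.96: centre = (p + z²/2n)/(1 + z²/n); half-width = z√(p(1−p)/n + z²/4n²)/(1 + z²/n). Here z²/2n = 0.0640 and 1 + z²/n = 1.1280.

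- All four counted: p = 4/30 = 13.3%; centre (0.1333 + 0.0640)/1.1280 = 0.175, half-width 0.122; interval 5.3% to 29.7%.
- Two counted: p = 2/30 = 6.7%; centre (0.0667 + 0.0640)/1.1280 = 0.116, half-width 0.097; interval 1.8% to 21.3%.

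The estimate halves, although the intervals overlap widely.

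**The case against.** The best reply is that an exception is not a contradiction. A specific carve-out qualifies a general table, and all that is missing is a cross-reference. This is a fair reading of intent, and the list may not have been written against Section 6 alone: its item on hospitalization for low-grade events matches no permanent-discontinuation entry there. But if the override is deliberate, a credited response still removes a DLT, with no criteria and no instruction on how to count the event.

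Three further points narrow the concern:

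- The event is not lost. Under Section 7.2 all adverse events are graded and recorded, and serious events of Grade 3 and above go to the monitoring committee whatever their cause. This stands. What is affected is the DLT count, and Section 12 attaches no rate or rule to DLTs.
- The table's title presents its contents as recommendations. That weakens calling its entries mandatory, but the governing sentence says that decisions will be made on the table, and the DLT definition depends on it.
- Section 5.1.1.3 bars restarting pembrolizumab during systemic corticosteroid treatment, apart from stable hormone replacement. So the exception does not mean uninterrupted dosing for a steroid-treated patient. It still leaves open whether the stop is permanent.

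**Conclusion.** The point stands in a limited form. For Grade 3 or recurrent Grade 2 pneumonitis that an investigator attributes to a local antitumor reaction, the protocol does not say whether treatment permanently stops, and DLT status depends on the answer. The effect is 3.3 points per reclassified patient if all 30 are in the denominator. How many patients would be affected cannot be derived from the documents. No stopping threshold changes; consistency of management and the reliability of the DLT count are at stake.

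A reader might infer more than the text supports:

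- **That Section 2.4 sets a third rule.** Its wording, "unacceptable toxicity (e.g., refractory Grade > 3 AEs", is an example given while describing who enters survival follow-up. It sets no discontinuation threshold.
- **That the exception names irradiated sites.** It does not. They may fall under it, because the listed examples are not exhaustive.
- **That every Grade 3 event is in conflict.** A first Grade 3 colitis and Grade 3 skin events are withheld, not stopped. Grade 3 nephritis is a permanent stop but fits poorly with a local tumor reaction.
- **That the pneumonitis frequency in Section 7.1.1 gives the size.** At 2–5%, 30 patients would yield 30 × 0.02 = 0.6 to 30 × 0.05 = 1.5 cases. That figure is for pneumonitis with pembrolizumab alone and is not limited by grade. The conflict needs a higher-grade or recurrent event that is local to tumor and credited to response.
- **That local inflammation is the toxicity the combination is most likely to add.** No section says so.

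**What to change.** Reconcile Sections 4.2, 5.1.1.3 and 6, including the DLT definition, and state which governs when they differ. Either the local-inflammation exception appears in the Section 6 rows it is meant to qualify, with its grade limits, or it does not operate on them. Which clinical rule is right is for the investigators; this review takes no view.

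Whichever rule is kept, separate counting from management. Amend the DLT definition, or add a line to the safety tabulation, so that every event meeting a permanent-discontinuation entry in Section 6 by type and grade is counted whether or not pembrolizumab was stopped. List separately those where dosing continued under an exception, with grade, site, whether the site was irradiated, and the attribution made. If the DLT definition is left as it stands, which requires actual discontinuation, the added line serves the same purpose under its own label.

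The cost is a short amendment, one extra row and listing in the safety report, and a DLT count that may look slightly less favorable.

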5.1.2 Radiation Therapy

Patients will receive palliative radiation therapy to 1-2 sites of disease. Radiation therapy will be delivered between the first and second cycles of anti-PD-1/PD-L1 therapy. The total dose and fractionation regimen of radiation will be determined by the attending physician by such factors as the location and size of the lesion that requires radiation, volume of radiosensitive normal tissue in the field, and clinical status of the patient. Patients will be treated with either 9 Gy X 3 (27 Gy in 3 fractions), or 4-6 Gy X 5 (20-30 Gy in 5 fractions). Radiation therapy will be planned in 3 or 4 D, and may be delivered using conventional, IMRT/ rapid arc or SBRT. Portal imaging for QC will occur according to SOC. All patients will be seen at least weekly by the attending physician while on treatment.

5.2 Availability

Both pembrolizumab and palliative radiation therapy are SOC.

5.3 Agent Ordering

Pembrolizumab will be obtained through the Stanford Hospital Pharmacy as SOC.

5.4 Agent Accountability

Pembrolizumab is FDA approved SOC therapy for Merkel cell carcinoma being dispensed from the Stanford Hospital Pharmacy and will not require accountability tracking.

6. DOSE MODIFICATIONS

Decisions to skip or modify a pembrolizumab dose will be made based on specified safety criteria as shown in the table below.

Recommended Dose Modifications of Pembrolizumab for Adverse Reactions

Treatment-Related Adverse Reaction	Severity of Adverse Reactions*	Dose Modification
Immune-Mediated Pneumonitis	Grade 2 pneumonitis	Withhold (a)
	Grade 3 or 4 pneumonitis or recurrent Grade 2 pneumonitis	Permanently discontinue.
Immune-Mediated Hepatitis	Aspartate aminotransferase (AST)/or alanine aminotransferase (ALT) more than 3 and up to 5 times the upper limit of normal or total bilirubin more than 1.5 and up to 3 times the upper limit of normal	Withhold Pembrolizumab. Resume Pembrolizumab in patients with complete or partial resolution (Grade 0 to 1) of hepatitis after corticosteroid taper.
	If no liver mets, AST or ALT more than 5 times the upper limit of normal or total bilirubin more than 3 times the upper limit of normal; if liver mets and grade 2 AST or ALT at baseline with at least 50% increase that persist for one week or more	Permanently discontinue.
Immune-Mediated Colitis		Withhold.
	Grade 2 or 3 diarrhea or colitis	Resume in patients with complete or partial resolution (Grade 0 to 1)

		of colitis or diarrhea after corticosteroid taper.
	Grade 4 diarrhea or colitis or recurrent Grade 3 diarrhea or colitis	Permanently discontinue.
Immune-Mediated Endocrinopathies (including but not limited to hypothyroidism, hyperthyroidism, adrenal insufficiency, hyperglycemia)	Grade 3 or 4	Withhold until clinically stable.
Immune-Mediated Nephritis and Renal Dysfunction	Grade 2	Withhold. Resume in patients with complete or partial resolution (Grade 0 to 1) of nephritis and renal dysfunction after corticosteroid taper.
	Grade 3 or 4	Permanently discontinue.
Other immune-mediated adverse reactions (including but not limited to myocarditis, myositis, psoriasis, arthritis, hypopituitarism, uveitis, Guillain-Barré syndrome, pancreatitis, rhabdomyolysis, myasthenia gravis, histiocytic necrotizing lymphadenitis, demyelination, vasculitis, hemolytic anemia, hypophysitis, iritis, and encephalitis) For Immune-mediated	For any of the following: Grade 2 or 3 based on severity and type Grade 3 based on severity and type or grade 4 Grade 3 or suspected Stevens-Johnson syndrome (SJS) or toxic epidermal necrolysis	Withhold (a) Permanently discontinue. Withhold

skin AEs	(TEN) Grade 4 or confirmed SJS or TEN	Permanently discontinue.
	For any of the following: Life-threatening adverse reaction (excluding endocrinopathies) Recurrent severe immune-mediated adverse reaction Requirement for 10 mg per day or greater prednisone or equivalent for more than 12 weeks Persistent Grade 2 or 3 immune-mediate adverse reactions lasting 12 weeks or longer	Permanently discontinue.
Infusion-related reaction	Grade 1 or 2	Interrupt or slow the rate of infusion.
	Grade 3 or 4	Permanently discontinue.

*Toxicity was graded per National Cancer Institute Common Terminology Criteria for Adverse Events. Version 5.0 (NCI CTCAE V5)

(a) Resume if complete or partial resolution (Grade 0, 1) after corticosteroid taper.

Dose Limiting Toxicity (DLT) Definition:

Dose limiting toxicity is when therapy is permanently discontinued due to toxicity as defined in the dose modification table above or when the patient withdraws from treatment due to toxicity that the patient finds unacceptable.

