4. TREATMENT PLAN

Screening/Baseline Visit

The following tests and examinations must be performed and the eligibility criteria satisfied before treatment may begin:

- Histologic diagnosis of Merkel Cell Carcinoma
- Demographics and medical history
- Measurements of weight, height, temperature, pulse, respiratory rate, and resting systolic and diastolic blood pressure
- Complete physical examination
- ECOG Performance Status
- Clinical laboratory tests:
 - Hematology: hemoglobin, hematocrit, CBC counts with differential (including absolute lymphocyte count) and direct platelet count
 - Serum Chemistry: albumin, serum alkaline phosphatase, SGOT (AST)/SGPT (ALT), total bilirubin, calcium, creatinine, glucose, lactate dehydrogenase (LDH), total protein, urea nitrogen (BUN), electrolytes (including sodium, potassium, chloride, and bicarbonate), TSH w/Reflex FT4
 - Urinalysis:
 - Gross examination including specific gravity, protein, glucose, and blood
 - Optional microscopic examination including WBC/HPF, RBC/HPF and any additional findings
- Optional Blood sample obtained for investigational immune response assays
- Chest radiography unless baseline CT scan was performed
- Electrocardiogram
- Relevant baseline radiographic images (e.g. brain, chest, abdomen, pelvis, and bone scans with the exact imaging studies utilized determined by the attending physician) within 6 weeks of initiation of anti-PD-1/PD-L1

- Current medications
- Baseline review of symptoms
- Pregnancy test
- Optional Tumor biopsy

Treatment Visits

The day subjects receive the first dose of pembrolizumab therapy will define Day 1. Subjects are required to have blood collected and chemistry labs analyzed up to 1 week prior to each dose of pembrolizumab. Investigators or an assigned medical professional must review liver function tests from the predosing labs and ensure the results meet dosing requirements prior to authorizing administration of each dose of pembrolizumab.

Subjects will receive a single dose of pembrolizumab as standard of care with 200mg IV every 3 weeks (with a -3 and +7-days window) until disease progression or unacceptable toxicity occurs.

During this treatment phase, the following procedures will be performed within 1 week of each scheduled visit:

- Pregnancy test for WOCBP, required within 6 weeks before first dose of pembrolizumab, then optional as clinically indicated for ongoing doses

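### Section 6 hepatitis rows: some liver-metastasis patients with treatment-related AST/ALT above 5 x ULN meet neither the withhold nor the discontinue row

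*Combined protocol and SAP*

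**What the plan says.** The hepatitis entry in Section 6 has two rows. The withhold row applies to AST/ALT "more than 3 and up to 5 times the upper limit of normal or total bilirubin more than 1.5 and up to 3 times" ULN and does not mention liver metastases, so it covers all patients. Its release condition is: "Resume Pembrolizumab in patients with complete or partial resolution (Grade 0 to 1) of hepatitis after corticosteroid taper".

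The permanent-discontinuation row has two clauses separated by a semicolon. The first reads "If no liver mets, AST or ALT more than 5 times the upper limit of normal or total bilirubin more than 3 times" ULN. The second reads "if liver mets and grade 2 AST or ALT at baseline with at least 50% increase that persist for one week or more".

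Section 6 gives the table authority over dosing: "Decisions to skip or modify a pembrolizumab dose will be made based on specified safety criteria as shown in the table below". It also builds the DLT definition on it: "Dose limiting toxicity is when therapy is permanently discontinued due to toxicity as defined in the dose modification table above", or patient withdrawal for toxicity the patient finds unacceptable.

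Inclusion criterion 3.1.7 admits patients with liver metastases at AST/ALT below 5 x ULN. Section 4 sets the sampling: "Subjects are required to have blood collected and chemistry labs analyzed up to 1 week prior to each dose of pembrolizumab", with doses every 3 weeks. It also requires liver tests to be checked against dosing requirements before each dose, but gives no thresholds of its own.

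**The concern.** A dose-modification table should not lose its instruction as the toxicity gets worse. Here the first discontinuation clause excludes patients with liver metastases, and the second brings back only a narrow subset of them. Staff who check pre-dose liver tests are in effect sent to Section 6 for the limits, and for some patients above 5 x ULN the hepatitis rows give none.

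What is at stake is consistent handling of a recognised immune toxicity in a trial with safety as a primary objective. A smaller consequence is that the same treatment-related AST of 8 x ULN is a table-defined DLT in a patient without liver metastases, but not in a patient with them who entered below Grade 2.

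**Working it through.** The plan has no figure to reproduce here. The check applies the two rows literally to a newly observed, treatment-related value in a patient not already on hold.

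**Inputs.** Withhold band: AST/ALT >3 to 5 x ULN (Section 6). General discontinuation limit: >5 x ULN, no liver metastases (Section 6). Liver-metastasis clause: Grade 2 at baseline, current value at least 1.5 x baseline, lasting one week or more (Section 6). Entry cap with liver metastases: <5 x ULN (3.1.7). Assumption: Grade 2 AST/ALT means >3 to 5 x ULN, matching the withhold band, because the documents give no numeric grade limits.

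**AST/ALT, bilirubin normal (values in x ULN).**

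| Liver metastases | Baseline | Current | Action in hepatitis rows |
|---|---|---|---|
| No | 1 | 4 | Withhold |
| No | 1 | 5.5, 7, 8, 19 | Discontinue |
| Yes | 1 or 2.5 | 4 | Withhold |
| Yes | 1 or 2.5 | 5.5, 7, 8, 19 | None |
| Yes | 4.0 | 5.5 | None |
| Yes | 4.0 | 7, 8, 19 | None until one week is shown, then discontinue |
| Yes | 4.9 | 5.5, 7 | None |
| Yes | 4.9 | 8, 19 | None until one week is shown, then discontinue |

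If bilirubin is itself >1.5 to 3 x ULN, the withhold row is triggered through bilirubin and the patient is held.

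**Group 1: liver metastases, below Grade 2 at baseline.** Every value above 5 x ULN falls outside both rows. The patient must get there without first being withheld in the 3 to 5 band, that is, by passing through the band between samples roughly 3 weeks apart.

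**Group 2: liver metastases, Grade 2 at baseline.** The uncovered range runs from just above 5 to just below 1.5 x baseline:
- entry 3.5: 1.5 x 3.5 = 5.25
- entry 4.0: 1.5 x 4.0 = 6.0
- entry 4.5: 1.5 x 4.5 = 6.75
- entry 4.9: 1.5 x 4.9 = 7.35

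This range opens when 1.5 x baseline > 5, i.e. baseline > 5/1.5 = 3.33 x ULN. It does not depend on the exact lower edge of Grade 2, provided that edge is at or below 3.33. Example: a move from 4.0 to 5.5 is a rise of 1.5/4.0 = 37.5%, which is above 5 x ULN but short of 50%. Where the rise does reach 50%, a single pre-dose sample cannot show that it has lasted a week, and the rows state no hold in the meantime.

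**Bilirubin.** If the no-liver-metastasis condition governs everything up to the semicolon, a liver-metastasis patient at 2 x ULN is withheld while one at 3.5 or 8 x ULN meets no hepatitis row. If the bilirubin limit is read as applying to all patients, this gap closes. The AST/ALT results above do not change under either reading.

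**The case against.** The strongest reply is that no patient would in practice be dosed at 8 x ULN without review. Section 4.2 requires discontinuation for any laboratory abnormality that the investigator judges makes continuing not in the patient's interest. The general items in Section 6 require discontinuation for life-threatening or recurrent severe reactions, prolonged steroid need, and Grade 2 or 3 immune reactions persisting 12 weeks or longer. The row for other immune-mediated reactions, which withholds at Grade 2 or 3 and discontinues at Grade 3 or 4 depending on severity and type, might be stretched to cover the liver. Most of this stands, and it is why the point is minor. But none of these gives a liver threshold or a clear hold for a first, non-life-threatening value just above 5 x ULN, and hepatitis has its own rows.

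Several stronger readings are tempting but not supported:

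- A reader might infer that a patient withheld at 4 x ULN is released on reaching 8. That is not so: the release condition is Grade 0 to 1, so the hold continues.
- A reader might infer that an eligible patient with raised baseline enzymes is caught at dose 1. Section 4 requires "the eligibility criteria satisfied before treatment may begin", and the table concerns treatment-related reactions.
- A reader might take the bilirubin gap as certain. The liver-metastasis clause names only AST/ALT, so the sentence can fairly be read as applying the bilirubin limit to everyone.
- A reader might infer that a Grade 2-baseline patient can never resume. If the resolution required is that of the immune event, recovery to entry level is enough; the text does not say which is meant.
- A reader might infer damage to the primary safety analysis. Section 12 has no DLT endpoint or stopping rule, and the toxicity counts and CTCAE grading do not depend on this table.

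It is also fair to say that the 50%/one-week clause is a deliberate tolerance for raised baselines, and that nothing forbids a repeat sample. That explains the clause but not the missing interim hold.

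**Conclusion.** The AST/ALT gap is real on the text: for group 1 at any value above 5 x ULN reached without a prior hold, and for group 2 up to 1.5 x baseline (at most 7.35 x ULN for entry at 4.9), or at higher values until a week's persistence is shown. The group 2 figures rest on taking Grade 2 as >3 to 5 x ULN. The bilirubin gap depends on the reading, and the resume wording is an ambiguity rather than an error.

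Severity is minor. The sample size of 30, the Wilson interval, the interim futility rule and the Section 12 analyses are unaffected, and the DLT consequence is small. No frequency is offered: the documents do not give the share of patients with liver metastases or the rate of values above these limits.

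**What to change.** Reword the discontinue row in Section 6:

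1. AST/ALT above 5 x ULN leads to permanent discontinuation in all patients except those with liver metastases and Grade 2 AST/ALT at baseline.
2. Those patients keep the 50%/one-week rule and are withheld for any treatment-related value above 5 x ULN until that rule is met or excluded.
3. Bilirubin above 3 x ULN is placed outside the no-liver-metastasis qualifier, so that it plainly applies to everyone.

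Optionally, state in the withhold row whether return to baseline is enough to resume when baseline was Grade 2. Criterion 3.1.7, the withhold thresholds and the DLT definition stay as they are.

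The cost is amendment wording, with no change to entry criteria, the scheduled tests or accrual. The downside is that a few more liver-metastasis patients may be withheld or discontinued, and those discontinued would count as DLTs. Item 1 is partly a clinical choice: withholding would also close the gap, but permanent discontinuation matches the limit the table already sets for patients without liver metastases.
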